For lab collections and procedures listed below, subjects/legal representatives will either visit their local Patient Service Center or mobile study personnel will be sent to the subject's/legal representative's home. Samples will be prepared and sent to a central laboratory for processing and analysis, and results will be provided to the study site.

- Safety laboratory tests
- Urine pregnancy test for all female subjects
- Hormone status

Has been changed to:

The assessments listed below will be completed by mobile study personnel at the subject's/legal representative's home and records of the procedures will be obtained, with information noted as part of the subject's study record.

- Brief physical examination, including body weight, height, BMI, and vital signs
- Neurological examination
- 12-lead ECG

For lab collections and procedures listed below, mobile study personnel will be sent to the subject's/legal representative's home. Samples will be prepared and sent to a central laboratory for processing and analysis, and results will be provided to the study site.

- Safety laboratory tests
- Urine pregnancy test for all female subjects
- Hormone status

Change #24

Section 8.7, Unscheduled Visit

The assessments listed below will be completed by the subject/subject's/legal representative's local healthcare provider and records of the procedures will be obtained, with information noted as part of the subject's study record.

- Brief physical examination, including body weight, height, BMI, and vital signs
- Neurological examination
- 12-lead ECG

For lab collections listed below, subjects/legal representatives will either visit their local Patient Service Center or mobile study personnel will be sent to the subject's/legal representative's home. Samples will be prepared and sent to a central laboratory for processing and analysis, and results will be provided to the study site.

- Vital signs
- Safety laboratory tests
- Urine pregnancy test for all female subjects
- Hormone status

Has been changed to:

The assessments listed below will be completed by mobile study personnel at the subject's/legal representative's home and records of the procedures will be obtained, with information noted as part of the subject's study record.

- Brief physical examination, including body weight, height, BMI, and vital signs
- Neurological examination

- 12-lead ECG

For lab collections and procedures listed below, mobile study personnel will be sent to the subject's/legal representative's home. Samples will be prepared and sent to a central laboratory for processing and analysis, and results will be provided to the study site.

- Vital signs
- Safety laboratory tests
- Urine drug screen
- Urine pregnancy test for all female subjects
- Hormone status

Change #25

Section 9.1, International Restless Legs Rating Scale (IRLS)

The IRLS will be performed at Screening, Baseline (Visit 2), and subsequent visits through Visit 8. The IRLS should also be performed in the event that a subject is prematurely withdrawn from the study (Withdrawal Visit).

Has been changed to:

The IRLS will be performed at Screening, Baseline (Visit 2), Visit 6, Visit 7, Visit 8, and Visit 9. The IRLS should also be performed in the event that a subject is prematurely withdrawn from the study (Withdrawal Visit).

Change #26

Section 11.6, Laboratory measurements

Table 11-2: Laboratory measurements

Hematology	Endocrine	Urinalysis
Red blood cell count	Estradiol ^a	Color
Hematocrit	FSH	Appearance
Hemoglobin	IGF-1	Glucose
Platelet count	LH	Protein
White blood cell count ^b	Progesterone ^a	Blood
	Prolactin	Ketones
	Testosterone ^c	Urine pregnancy test ^a
	T3	
	T4	
	TSH	
Chemistry		
ALT	Glucose	
AST	Phosphorus	
Albumin	LDH	
Alkaline phosphatase	Potassium	
Bicarbonate	Serum iron	
BUN	Sodium	
Calcium	Total cholesterol	
Chloride	Total bilirubin	
Creatinine	Total protein	
Ferritin	Transferrin	
GGT	Uric acid	

ALT=alanine aminotransferase; AST=aspartate aminotransferase; BUN=blood urea nitrogen; FSH=follicle-stimulating hormone; GGT=gamma-glutamyl transferase; IGF-1=insulin-like growth factor-1; LDH=lactate dehydrogenase; LH=luteinizing hormone; T3= triiodothyronine; T4=thyroxine; TSH=thyroid-stimulating hormone

^a Females only

^b With differential

^c Males only

Has been changed to:

Table 11-2: Laboratory measurements

Hematology	Endocrine	Urinalysis
Red blood cell count	Estradiol ^a	Color
Hematocrit	FSH	Appearance
Hemoglobin	IGF-1	Glucose
Platelet count	LH	Protein
White blood cell count ^b	Progesterone ^a	Blood
RBC indices	Prolactin	Ketones
MCH	Testosterone ^c	Pregnancy test ^a
MCV	T3	
MCHC	T4	
RDW	TSH	
Chemistry		
ALT	Glucose	
AST	Phosphorus	
Albumin	LDH	
Alkaline phosphatase	Potassium	
Bicarbonate	Serum iron	
BUN	Sodium	
Calcium	Total cholesterol	
Chloride	Total bilirubin	
Creatinine	Total protein	
Ferritin	Transferrin	
GGT	Uric acid	

ALT=alanine aminotransferase; AST=aspartate aminotransferase; BUN=blood urea nitrogen; FSH=follicle-stimulating hormone; GGT=gamma-glutamyl transferase; IGF-1=insulin-like growth factor-1; LDH=lactate dehydrogenase; LH=luteinizing hormone; MCH=mean corpuscular hemoglobin; MCHC= mean corpuscular hemoglobin concentration; MCV=mean cell volume; RBC=red blood cell; RDW=red cell distribution width; T3=triiodothyronine; T4=thyroxine; TSH=thyroid-stimulating hormone

^a Females only. Serum pregnancy test at Screening and urine pregnancy test at all other visits. A positive urine pregnancy test must be confirmed by a serum pregnancy test.

^b With differential.

^c Males only.

17.2 Protocol Amendment 2

Rationale for the amendment

The protocol has been amended for the following reasons:

- Change the sponsor company name from “UCB Biopharma SPRL” to “UCB Biopharma SRL” since the name of the legal form of the entity UCB Biopharma has changed into “société à responsabilité limitée” abbreviated “SRL”.

PUBLIC COPY
This document cannot be used to support any marketing authorization application and any extensions or variations thereof.

17.3 Protocol Amendment 3

Rationale for the amendment

The main purpose of this amendment was to change the shipment of study medication and all required supplies from the study site to the study site's depot/pharmacy.

Other changes included in this amendment are as follows:

- Principal Investigator and Sponsor contact information has been updated.
- Changed Network Oriented Research Assistant (NORA[®]) to Science 37 Platform (PLATFORM).
- Clarified that the Baseline for the other safety variables is Visit 1.

Modifications and changes

Global changes

The following changes have been made throughout the protocol:

- Changed Network Oriented Research Assistant (NORA[®]) to Science 37 Platform (PLATFORM) throughout the protocol.

Specific changes

Change #1

STUDY CONTACT INFORMATION:

Sponsor

UCB BIOSCIENCES Inc., [name]

Principal/Coordinating Investigator

Name:	[name], [REDACTED]
Affiliation:	Science 37
Address:	[name], [REDACTED] [name]
Phone:	[REDACTED]

Sponsor Study Physician

Name:	[REDACTED]
Address:	UCB BIOSCIENCES GmbH [name]
Phone:	[REDACTED]
Email:	[REDACTED]

Clinical Project Manager

Name:	██████████
Address:	UCB Biosciences Inc. [name]
Phone:	██████████
Email:	████████████████████

Clinical Trial Biostatistician

Name:	██████████
Address:	UCB Celltech [name]
Phone:	██████████
Email:	████████████████████

Has been changed to:

Sponsor

UCB Biopharma SRL, [name]

Principal/Coordinating Investigator

Name:	[name], ██████
Affiliation:	Science 37
Address:	[name], ██████ [name]
Phone:	██████████

Sponsor Study Physician

Name:	████████████████████
Address:	UCB Biosciences Inc. [name], ██████████ [name]
Phone:	████████████████████
Email:	████████████████████

Clinical Project Manager

Name:	████████████████████
Address:	UCB Biosciences Inc. [name], ██████████ [name]
Phone:	████████████████████
Email:	████████████████████

Clinical Trial Biostatistician

Name:	████████████████████
Address:	UCB Biosciences Inc. [name], ██████████ [name]
Phone:	████████████████████
Email:	████████████████████

Change #2

Section 4.2.2, Other safety variables

- Changes from Baseline in 12-lead ECGs
- Changes from Baseline in vital signs (including assessment of orthostasis)
- Changes from Baseline in laboratory data (hematology, blood chemistry, and urinalysis)
- Changes from Baseline in hormone status

- Changes from Screening in body weight, height, and BMI
- Changes from Baseline in mMIDI
- Changes in menstrual function for all female subjects

Has been changed to:

- Changes from Baseline (Visit 1) in 12-lead ECGs
- Changes from Baseline (Visit 1) in vital signs (including assessment of orthostasis)
- Changes from Baseline (Visit 1) in laboratory data (hematology, blood chemistry, and urinalysis)
- Changes from Baseline (Visit 1) in hormone status
- Changes from Baseline (Visit 1) in body weight, height, and BMI
- Changes in mMIDI
- Changes in menstrual function for all female subjects

Change #3

Section 5.1, Study description

Fourth paragraph

The study will begin with a Screening Period of at least 7 days (maximum of 28 days) prior to Visit 2/Baseline to ensure homogeneous baseline conditions can be established for all subjects. Subjects with prior intake of any dopamine agonists must discontinue the therapy at least 14 days prior to Visit 2/Baseline. Subjects taking L-dopa must discontinue the therapy at least 7 days prior to Visit 2/Baseline. Discontinuation of therapy must be driven by the subject's medical need and not undertaken for the purpose of making a potential subject eligible for the study.

Has been changed to:

The study will begin with a Screening Period of at least 7 days (maximum of 28 days) prior to Visit 2/Baseline to ensure homogeneous baseline conditions can be established for all subjects. Subjects with prior intake of any dopamine agonists or taking L-dopa must discontinue the therapy at least 7 days prior to Visit 2/Baseline. Discontinuation of therapy must be driven by the subject's medical need and not undertaken for the purpose of making a potential subject eligible for the study.

Change #4

Section 7.5, Handling and storage requirements

First and fourth paragraphs

Rotigotine transdermal patches should be stored in the original pouch. Rotigotine should be stored according to the labeling on the clinical trial supply packaging. The investigator (or designee) is responsible for the safe and proper storage of rotigotine at the site. Rotigotine stored by the investigator is to be kept in a secured area with limited access according to the storage conditions mentioned on the label.

As part of the remote study model, the study site will provide study medication and all required supplies via direct-to-subject shipments. Once eligibility is confirmed, the study site will contact the interactive response technology (IRT) for randomization assignment, and shipments will be prepared and sent out for delivery to the subject's/legal representative's home/preferred address. Shipments will be confirmed as delivered by the study staff, with appropriate documentation in the subject's study records. The study medication will be confirmed as received in good condition and within the acceptable temperature range (ie, fit for use). A telemedicine call will be completed to instruct the subject/legal representative on the correct storage and administration of the study medication, which will also be documented as part of subject's study record.

Has been changed to:

Rotigotine transdermal patches should be stored in the original pouch. Rotigotine should be stored according to the labeling on the clinical trial supply packaging. The investigator (or designee) is responsible for the safe and proper storage of rotigotine at the site. Rotigotine stored by the investigator (or designee) is to be kept in a secured area with limited access according to the storage conditions mentioned on the label.

As part of the remote study model, the study site's depot/pharmacy will provide study medication and all required supplies via direct-to-subject shipments. Once eligibility is confirmed, the study site will contact the interactive response technology (IRT) for randomization assignment, and shipments will be prepared and sent out for delivery to the subject's/legal representative's home/preferred address. Shipments will be confirmed as delivered by the study staff, with appropriate documentation in the subject's study records. The study medication will be confirmed as received in good condition and within the acceptable temperature range (ie, fit for use). A telemedicine call will be completed to instruct the subject/legal representative on the correct storage and administration of the study medication, which will also be documented as part of subject's study record.

Change #5

Section 7.6, Drug accountability

First and third paragraphs

At the designated timepoints during the study, subjects/legal representatives will return to the study site the unused study medication patches remaining as part of the medication kits, along with the kit itself, via the return shipment materials provided. A Drug Accountability form will be used to record IMP dispensing and return information on a by subject basis and will serve as source documentation during the course of the study. Details of any IMP lost, damaged (due to breakage or wastage), not used, disposed of at the study site, or returned to the sponsor or designee must also be recorded on the appropriate forms. All supplies and drug accountability documentation must be made available throughout the study for UCB (or designee) to review.

The investigator may assign some of the investigator's duties for drug accountability at the study site to an appropriate designee.

Has been changed to:

At the designated timepoints during the study, subjects/legal representatives will return to the study site's depot/pharmacy the unused study medication patches remaining as part of the medication kits, along with the kit itself, via the return shipment materials provided. A Drug

Accountability form will be used to record IMP dispensing and return information on a by subject basis and will serve as source documentation during the course of the study. Details of any IMP lost, damaged (due to breakage or wastage), not used, disposed of at the study site's depot/pharmacy, or returned to the sponsor or designee must also be recorded on the appropriate forms. All supplies and drug accountability documentation must be made available throughout the study for UCB (or designee) to review.

The investigator may assign some of the investigator's duties for drug accountability at the study site's depot/pharmacy to an appropriate designee.

Change #6

Section 7.7, Procedures for monitoring subject compliance

First paragraph

At the designated visits (see [Table 5-1](#)), subjects/legal representatives will return all unused IMP and empty IMP containers, using the return shipment supplies provided to them by the study staff. Upon receipt of the returned medication at the study site, the designated study staff will review drug accountability with the subject/legal representative via a telephone or a telemedicine call in order to obtain explanations regarding any discrepancies in compliance with the dosing regimen.

Has been changed to:

At the designated visits (see [Table 5-1](#)), subjects/legal representatives will return all unused IMP and empty IMP containers, using the return shipment supplies provided to them by the study staff. Upon receipt of the returned medication at the study site's depot/pharmacy, the designated study staff will review drug accountability with the subject/legal representative via a telephone or a telemedicine call in order to obtain explanations regarding any discrepancies in compliance with the dosing regimen.

RS	Randomized Set
SAP	Statistical Analysis Plan
SD	standard deviation
SOC	System Organ Class
SS	Safety Set
T3	triiodothyronine
T4FR	thyroxine free
TEAE	treatment-emergent adverse event
TSH	thyroid-stimulating hormone
ULN	upper limit of normal
WHO-DD	World Health Organization Drug Dictionary

PUBLIC COPY
This document cannot be used to support any marketing authorization application and any extensions or variations thereof.

1 INTRODUCTION

This document contains details for the statistical analyses of study SP1006 which has been written in consideration of the International Council for Harmonization (ICH)/Food and Drug Administration (FDA) E9 Guidance documents (Phillips et al, 2003). The reader is referred to the study protocol and the electronic Case Report form (eCRF) for details of study conduct and data collection.

The Statistical Analysis Plan (SAP) describes the statistical principles that will be applied for the analyses as well as tables and listings that are foreseen for this study. Changes in the statistical methodology will result in an SAP amendment. Amendments to this document will be finalized prior to database lock.

This study was terminated early, and therefore the analysis described in this analysis plan is much more limited than that described in the protocol.

2 PROTOCOL SUMMARY

2.1 Study objectives

2.1.1 Primary objective

To demonstrate the efficacy of rotigotine against placebo in adolescent subjects with idiopathic Restless Legs Syndrome (RLS) over a 12-week Maintenance Period.

2.1.2 Secondary objectives

To investigate the safety and tolerability of rotigotine in adolescent subjects with idiopathic RLS.

2.2 Study variables

2.2.1 Efficacy variables

2.2.1.1 Primary efficacy variable

- Change from Baseline in International Restless Legs Rating Scale (IRLS) sum score at end of the Maintenance Period (EoM)
- Change from Baseline in Clinical Global Impressions (CGI) Item 1 at EoM

2.2.1.2 Secondary efficacy variables

- Change from Baseline in Restless Legs-6 Rating Scales (RLS-6) at EoM

2.2.1.3 Other efficacy variables

- Change from Baseline in CGI Item 1 by visit*
- Change from Baseline in RLS-6 Rating Scales by visit*
- Change from Baseline in IRLS sum score by visit*

* For the IRLS, CGI, and RLS-6 the EoM visit is already covered under primary and secondary variables.

2.2.2 Safety variables

- Occurrence of treatment emergent adverse events (TEAEs)

- TEAEs leading to withdrawal
- Changes from Baseline in 12-lead electrocardiograms (ECGs)
- Changes from Baseline in vital signs (including orthostatic assessment)
- Changes from Baseline in laboratory data (hematology, blood chemistry, and urinalysis)
- Changes from Baseline in hormone status
- Changes from Screening in body weight, height, and calculated body mass index (BMI)
- Changes from Baseline in Modified Minnesota Impulsive Disorder Interview (mMIDI)
- Changes in menstrual function for all female subjects

2.2.3 Other variables

- Plasma concentrations of unconjugated rotigotine
- Subject Quality of Life Questionnaire

2.3 Study design and conduct

This is a Phase 3, remote, double-blind, randomized, adaptive placebo-controlled study of fixed dose administration of the rotigotine transdermal system. The study will be conducted in adolescent subjects, 13 to 17 years of age, with idiopathic RLS. Subjects will be randomized to 1 of 3 treatment groups: placebo, 2mg/24h rotigotine, or 3mg/24h rotigotine.

The study will be conducted using the remote study model, which uses telemedicine technology (i.e., Science 37 PLATFORM) for interactions between the investigator/study staff and study subjects/legal representatives. Mobile study personnel will visit subjects'/legal representatives' homes to complete certain study procedures (e.g., neurological exams, physical exams, ECGs, lab collections, and vital signs).

The study will begin with a Screening Period of at least 7 days (maximum of 28 days) prior to Visit 2/Baseline to ensure homogeneous baseline conditions can be established for all subjects. Subjects with prior intake of any dopamine agonists must discontinue therapy at least 14 days prior to Visit 2/Baseline. Subjects taking L-dopa must discontinue therapy at least 7 days prior to Visit 2/Baseline.

The Screening Period will be followed by the Titration Period. Subjects will receive their first dose of study medication at Visit 3/Day 1. Subjects will be initiated either on placebo or 1mg/24h rotigotine. The dose of rotigotine taken by subjects randomized to rotigotine will then be up-titrated on a weekly basis by 1mg/24h at a time to 2mg/24h or 3mg/24h, depending on the subject's assigned dose level.

Subjects will be allowed to back-titrate one dose level during the Titration Period. Subjects are to complete the Titration Period at the back-titrated dose level and remain at this dose level for the duration of the Maintenance Period. Subjects who do not tolerate the assigned dose in the first week (placebo or 1mg/24h) will be withdrawn from the study. If subjects withdraw due to lack of efficacy, they are eligible to roll-over to the open-label study, RL0007, after the 3 weeks of the Titration Period are completed.

The Titration Period will be followed by a 12-week Maintenance Period. Subjects will remain at the assigned (or back-titrated) dose level throughout the Maintenance Period. At the end of the Maintenance Period, subjects will enter a Taper Period lasting up to a maximum of 4 days (de-escalation of study medication), followed by a 30-day Safety Follow-Up Period.

Visits will be scheduled every week during the Titration Period. During the Maintenance Period, visits will be scheduled every 4 weeks. There is a 4-day interval until the end of the Taper period, followed by a 30-day interval (± 5 days) until the Safety Follow-Up Visit.

2.4 Adaptations due to interim analysis decision

Due to early stopping of the study, this section is no longer applicable.

2.5 Determination of sample size

The sample size estimate is based on the efficacy results observed in the adult RLS Phase 3 confirmatory trial SP792, which was conducted in the USA. In this study, a range of rotigotine doses were compared to placebo.

The sample size computation assumes that adolescent and adult patients will show a similar effect of rotigotine with respect to IRLS score and CGI (Item 1) changes from Baseline in comparison to placebo, with a similar proportion of patients not included in the primary analysis.

In the adult study, the observed difference between the 3mg/24h rotigotine group and placebo in the Change from Baseline to end of 3-month Maintenance Period in IRLS sum score was 5.9. A difference between rotigotine and placebo of 4.0 can be considered as clinically relevant. The common standard deviation (SD) estimate in the adult study was 7.9. For the CGI Item 1, the difference between 3mg/24h rotigotine group and placebo was 0.8 with a SD of 1.2.

With these assumptions, a total sample size of 45 evaluable patients in each group will provide a power of 93% for the IRLS endpoint, and a power of 87% for the CGI (Item 1) endpoint in the analysis of the 3mg/24h dose. Assuming independence of the 2 endpoints will result in a power of 80% for the analysis of the co-primary variables. Since it is known that the 2 endpoints will have a relatively high correlation (approximately 0.7), the calculated 80% is a conservative estimator for the power.

Assuming similar effects for the 2mg/24h dose group, the conditional power for the 2mg/24h dose group is also 80% with an overall power for the study $>60\%$. To obtain 135 evaluable patients (i.e., FAS), 138 patients must be randomized (assuming approximately 2% of the randomized patients cannot be utilized).

3 DATA ANALYSIS CONSIDERATIONS

3.1 General presentation of summaries and analyses

Statistical analysis and generation of tables, figures, subject data listings, and statistical output will be performed using SAS Version 9.3 or higher. All tables and listings will use Courier New font size 9.

A complete set of raw data listings containing both all documented data and all calculated data (e.g., changes from Baseline) will be generated.

Unless otherwise noted, all summaries will be displayed by randomized treatment group (placebo, rotigotine 2mg/24h and rotigotine 3mg/24h, respectively) regardless of the doses individual subjects received. A summary with all treatment groups combined (i.e., total column) will be presented for the demographic and Baseline characteristics, for the prior medications, as well as for the medical history.

In general, summary statistics for quantitative variables will include n (number of available measurements), arithmetic mean, SD, median, minimum, and maximum. For categorical parameters, descriptive statistics will consist of the number and percentage of subjects in each category. Unless otherwise specified the denominator for calculating percentages will be the number of subjects in the respective population.

Unless otherwise noted, all percentages with the exception of 0 and 100 will be expressed to 1 decimal place. 100% will be presented as integer. If a category has the frequency 0 the percentage value will be omitted. Mean and median changes from baseline lower than the minimal displayable change will be displayed without sign (e.g., -0.00 will be displayed as 0.00).

For descriptive statistics, the following rules regarding decimal places will apply:

- n will be an integer.
- Mean, SD, and median will use 1 additional decimal place compared to the original data.
- Minimum and maximum will have the same number of decimal places as the original value.

Unless otherwise noted, listings will be sorted by randomized treatment, site-subject number, parameter (if applicable) and time point (if applicable). All listings will include assessments on scheduled and unscheduled visits; data from unscheduled visits will appear in chronological order together with the scheduled time points – a repeated measurement will appear directly after the time point for which the repeat measurement was performed.

In individual subject data listings, values are presented as documented in eCRF using the same number of digits. Derived data are presented with 1 digit more than the original data used in the derivation. Dates are presented as documented without imputing incomplete dates.

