8.5 Safety Follow-Up Visit (if applicable)

The visit window for Safety Follow-Up Period is 30 days \pm 5 days relative to the end of the Taper Period. Following dose de-escalation, subjects may be eligible to participate in the open-label, long-term follow-up study (RL0007) at any time prior to the Safety Follow-Up Visit (see [Section 5](#)). The Safety Follow-Up Visit is for subjects not entering RL0007.

Information listed below will be collected by the investigator and/or study staff, as appropriate, via a telephone or telemedicine call with the subject/legal representative.

- Menstrual function for all female subjects

The assessments listed below will be completed by mobile study personnel at the subject's/legal representative's home and records of the procedures will be obtained, with information noted as part of the subject's study record.

- Brief physical examination, including body weight, height, BMI, and vital signs
- Neurological examination
- 12-lead ECG

For lab collections and procedures listed below, mobile study personnel will be sent to the subject's/legal representative's home. Samples will be prepared and sent to a central laboratory for processing and analysis, and results will be provided to the study site.

- Safety laboratory tests
- Urine pregnancy test for all female subjects
- Hormone status

Assessments listed below will be completed either by the subject or investigator/trained study staff, as required. Assessments that require interviews will be completed via a telephone or telemedicine call.

- C-SSRS (Since Last Visit version)

Additional assessments and procedures are listed below.

- Recording of medication and procedures. See [Section 8.2.1](#).
- AE assessment. See [Section 8.2.1](#).
- Contact IRT. The IRT is contacted to process the subject's completion of the study.
- Return unused study medication. See [Section 8.3.1](#).

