3.5.3 Safety Set (SS)

The SS will consist of all subjects from the RS who have at least one patch (rotigotine or placebo) applied. This population will be used for safety analysis.

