10 SAFETY ANALYSES

If not stated otherwise, all safety analyses will be conducted for the SS.

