10.3 Clinical laboratory evaluations

The following laboratory parameters are measured within the study:

- Hematology parameters: Hematocrit, Hemoglobin, Platelets, Red Blood Cells, White Blood Cells, and differential count and percentile (Lymphocytes, Basophils, Eosinophils, Monocytes, Neutrophils)
- Liver Function Tests and other Chemistry parameters: Alanine Aminotransferase (ALT), Aspartate Transaminase (AST), Albumin, Alkaline Phosphatase (ALP), Bicarbonate, Blood Urea Nitrogen, Calcium, Chloride Creatinine, Ferritin, Gamma-glutamyl transferase, Glucose, Iron Binding Capacity Total, Iron Binding Capacity Unsaturated, Lactate Dehydrogenase, Potassium, Phosphorus, Serum Iron, Sodium, Total cholesterol, Total bilirubin, Total protein, Transferrin, Uric acid
- Endocrine parameters: Estradiol (females only), Follicle-stimulating Hormone (FSH), Insulin-like Growth Factor 1 (IGF-1), Luteinizing Hormone (LH), Progesterone (females)

only), Prolactin, Testosterone (males only), Thyroxine Free (T4FR), Triiodothyronine (T3), Thyroid Stimulating Hormone (TSH)

– Endocrine normal ranges are provided by the central lab and included in the dataset specifications.

- Urinalysis: Color, Appearance, Glucose, Protein, Blood, Ketones, Urine Pregnancy Test

Summary statistics of the observed values and their change from Baseline and the frequency of abnormal values based on normal ranges will be presented by visit for laboratory parameters of hematology, chemistry and endocrinology.

Laboratory data outside the reference range will be highlighted with “L” for low and “H” for high in all laboratory subject data listings where applicable. Individual subject data listings will be presented for laboratory parameters of hematology, chemistry and endocrinology. Urinalysis and pregnancy test results will only be listed.

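### SAP 10.3 does not override the full-population denominator, so by-visit laboratory abnormality percentages count untested subjects, including the other sex for sex-specific hormones, as not abnormal

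*SAP*

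**What the plan says.** - **Default denominator.** SAP 3.1: "Unless otherwise specified the denominator for calculating percentages will be the number of subjects in the respective population".
- **Form of categorical summaries.** SAP 3.1: "For categorical parameters, descriptive statistics will consist of the number and percentage of subjects in each category".
- **Population.** SAP 10: "If not stated otherwise, all safety analyses will be conducted for the SS". SAP 3.5.3: "The SS will consist of all subjects from the RS who have at least one patch (rotigotine or placebo) applied". Membership therefore requires one patch and no laboratory sample.
- **Laboratory output.** SAP 10.3 says that "the frequency of abnormal values based on normal ranges will be presented by visit for laboratory parameters of hematology, chemistry and endocrinology". It gives no denominator, no restriction by sex and no category for missing or not applicable.
- **Sex-specific hormones.** In the endocrine list of SAP 10.3, the testosterone entry begins "Testosterone (males only" and the estradiol entry begins "Estradiol (females only), Follicle-stimulating Hormone (FSH". Progesterone is also marked as measured in females. Protocol 6.1 admits both sexes.
- **Safety Follow-Up.** Protocol 8.5 schedules safety laboratory tests and hormone status at this visit, but "The Safety Follow-Up Visit is for subjects not entering RL0007".
- **Missing safety data.** Protocol 13.6 says that missing safety values are not imputed.

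**The concern.** A by-visit abnormality percentage is normally read as the share of tested subjects whose value was outside the normal range. Under the default rule it is the share of everyone in the arm who ever applied a patch. A subject with no result cannot enter the numerator but stays in the denominator, and so is treated as not abnormal. That sits badly with the protocol's decision not to impute missing safety values.

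Two groups without a result are built into the design and need no assumption about dropout. The first is the other sex, for the three sex-specific hormones. The second is the RL0007 entrants at Safety Follow-Up. At stake is whether the printed hormone and laboratory percentages can be taken at face value in a study of adolescents in which hormone status is a named safety variable.

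**Working it through.** The documents state no abnormality rate, sex split or number sampled, so there is no figure of the plan's own to reproduce. The check has two parts.

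**1. Does the rule reach these tables?** SAP 3.1 applies unless something else is specified. SAP 10 supplies the SS as the population. SAP 10.3 specifies no alternative. SAP 6.1, by contrast, lists a Missing category for BMI, which keeps a full-population denominator readable; 10.3 has no equivalent. The rule therefore applies to any percentage printed there.

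**2. How large is the effect?** Let N be the SS subjects in an arm, n those with a result for the parameter at the visit, and x those with an abnormal result.

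- Displayed rate = x / N
- Rate among those assessed = x / n
- Hence displayed rate = (x / n) × (n / N)

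The shortfall factor n / N does not depend on the size of the arm. For illustration take N = 138 / 3 = 46, which is the planned number randomized split equally. Early termination may make the actual number smaller. Sampling fractions, sex splits and the 20% rate are assumptions.

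*Both-sex parameter, 20% abnormal among those assessed:*

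| Assessed n of 46 | Displayed |
|---|---|
| 46 (100%) | 20.0% |
| 41 (about 90%) | 0.20 × 41/46 = 17.8% |
| 37 (about 80%) | 0.20 × 37/46 = 16.1% |
| 32 (about 70%) | 0.20 × 32/46 = 13.9% |
| 23 (50%) | 0.20 × 23/46 = 10.0% |

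The last row is also what Safety Follow-Up would show if half of an arm entered RL0007 and everyone else was sampled.

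*Sex-specific hormone, 20% abnormal among those assessed:*

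| Applicable sex as share of arm | All of them sampled | 80% of them sampled |
|---|---|---|
| 40% | 0.20 × 0.40 = 8.0% | 6.4% |
| 50% | 0.20 × 0.50 = 10.0% | 8.0% |
| 60% | 0.20 × 0.60 = 12.0% | 9.6% |

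With a true rate of 10%, every displayed value in both tables halves.

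*Whole-number example.* Four abnormal results in an arm of 46 print as 4/46 = 8.7%. If 37 were assessed, the rate among them is 4/37 = 10.8%. If the 23 subjects of the applicable sex were all assessed, it is 4/23 = 17.4%. If 18 of them were assessed, it is 4/18 = 22.2%.

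*Between arms.* If 41 of 46 were sampled in one arm and 32 of 46 in another, equal rates of 20% would print as 17.8% and 13.9%. This shows the mechanism only. The documents give no attendance by arm.

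**The case against.** **No percentage is specified.** SAP 10.3 promises a *frequency*, and SAP 3.1 uses that word for a count in its rule on zero categories. Where the documents want both count and percentage they usually say so, as for adverse events and medications. The table shells are not available and may already use subjects with a result. This stands as a reason to word the point conditionally. It does not remove it, because the categorical rule in SAP 3.1 calls for both number and percentage, and Protocol 13.4.1 describes its adverse event frequency tables in those terms. A percentage is the natural reading.

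**The right rate can be recovered.** SAP 10.3 pairs the abnormality frequencies with summary statistics by visit, which under SAP 3.1 include the number of available measurements. Values are also listed by subject with low and high flags. This is correct and limits the harm, but the printed percentage would still mislead a reader who does not recompute it.

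**Missing Visit 9 samples.** A reader might infer from early termination and withdrawals that many SS subjects lack a Visit 9 sample. The documents do not support that. Protocol 8.6 gives the Withdrawal Visit the same procedures as Visit 9, including laboratory tests and hormones, and SAP 3.2.3 records them on the Visit 9 pages. SAP 4.2 attributes off-schedule discontinuation data to the next scheduled visit in by-visit endpoint summaries. If that covers laboratory data, some withdrawal samples would be shown under another visit. Neither document gives a number without a Visit 9 result.

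**Importance.** A reader might also treat these percentages as central safety results. Protocol 4.2.1 makes treatment-emergent adverse events the primary safety variables. Laboratory data and hormone status fall under other safety variables in 4.2.2 and are defined as changes from Baseline, which this rule does not touch.

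**Conclusion.** The point holds in a limited form. As written, the SAP directs that any by-visit laboratory abnormality percentage be taken over the whole SS arm. For estradiol, progesterone and testosterone this understates the rate in any arm that contains both sexes and has at least one abnormal result, even with perfect attendance. At Safety Follow-Up it understates the rate in any arm that has RL0007 entrants and at least one abnormal result. Elsewhere it does so only to the extent that results are missing. Where every SS subject has a result for a both-sex parameter, nothing is lost.

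The size is exactly the factor n / N. The numerical illustrations rest on assumed sex splits, sampling fractions and abnormality rates. A claim that the rule has created or hidden a difference between arms would go beyond the documents. No hypothesis test or decision rule uses these percentages, so this is a correction to descriptive safety reporting.

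**What to change.** Add to SAP 10.3: for by-visit abnormality percentages, the denominator is the number of SS subjects with a non-missing result for that parameter at that visit, restricted to the applicable sex for sex-specific hormones, and this n is displayed with the count.

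The cost is one sentence and a change of denominator in the table program, with no new data. The SAP introduction allows amendments until database lock. If the table shells already work this way, the sentence brings the SAP into line with them.
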